4.3 Removal of patients from therapy / study

4.3.1 Regular termination of study participation

The participation of the patient in the study is regularly terminated:

1. In case of death or in case of lymphoma failure
2. Discontinuation of study drug due to toxicity or adverse event

4.3.2 Premature termination of study participation

The patient may drop out of the clinical study at any time without stating reasons. This may not have any negative consequences for the patient’s further treatment.

Possible reasons for withdrawal of the patient are:

- Withdrawal of the patient’s consent
- Further participation assessed by the investigator to be unacceptable / intolerable
- Pregnancy
- Lack of co-operation/compliance of the patient
- Occurrence of new diseases that could influence the treatment efficacy, for which the study medication is contraindicated or that are treated with a medication that is not permitted as a concomitant medication.
- Reconsideration of the risk/benefit ratio, in consensus with Ethical Committee and Independent Safety Monitoring Committee

The reason for both regular and premature termination should be recorded in the CRF and in the subject’s medical records.

5 Treatment Plan

5.1 Treatment

After the documentation of PR or CR after salvage chemo-immunotherapy, patients will receive lenalidomide 25 mg daily orally for 21 days every 28 days for 2 years (24 cycles). This maintenance therapy will start after one month from salvage chemotherapy conclusion. The duration of period between the end of chemotherapy and the beginning of maintenance treatment can be variable according to the achievement of the acceptable haematological and biochemical parameters. This interval could be prolonged until the patient will be considered eligible for the trial, within 2 months.

5.2 Identity of investigational product

Celgene Corporation will supply 10 mg, 5 mg and 25 mg lenalidomide capsules for oral administration in order to treat patients with the full dose of 25 mg and in case to adjust this dose if any drug related AEs occur.

Lenalidomide will be packaged in bottles containing 21 days of study drug.

5.3 Dose Modification or Interruption

Dose reduction levels are reported on Appendix I.

Subjects will be evaluated for AEs at each visit following the NCI CTCAE (Version 3.0) and used as a guide for the grading of severity:

- Thrombocytopenia will be graded as follows:
 - Grade 1 $\geq 75 \times 10^9/L$ and $< LLN$
 - Grade 2 ≥ 50 and $< 75 \times 10^9/L$
 - Grade 3 ≥ 25 and $< 50 \times 10^9/L$
 - Grade 4 $< 25 \times 10^9/L$
- Hemoglobin will be graded as follows:
 - Grade 1 $\geq 10 \text{ g/dL}$ and $< LLN$
 - Grade 2 ≥ 8 and $< 10 \text{ g/dL}$
 - Grade 3 ≥ 6.5 and $< 8 \text{ g/dL}$
 - Grade 4 $< 6.5 \text{ g/dL}$
- Neutropenia will be graded as follows: (ANC/ μ L)
 - Grade 1 ≥ 1500 and $< 2000 \times 10^9/L$
 - Grade 2 ≥ 1000 and $< 1500 \times 10^9/L$
 - Grade 3 ≥ 500 and $< 1000 \times 10^9/L$
 - Grade 4 $< 500 \times 10^9/L$

5.4 Prior/Concomitant Medications

All medications (prescription and non-prescription), treatments and therapies taken during the treatment with study drug must be recorded on the appropriate CRF.

All the therapies considered necessary for the subject's wellbeing may be administered at the discretion of the Investigator. These therapies may include antibiotics, analgesics, antihistamines, or other medications as well as growth factors and transfusions of red blood cells, platelets, or fresh frozen plasma given to assist in the management of complications associated with NHL or its therapy. To date, no data on a higher risk of thromboembolic complications with lenalidomide in lymphoma patients have been reported. However, antithrombotic prophylaxis could be indicated according to the Institutional guidelines of each center and o the individual risk of the registered patient considering that patients entering into this trial will be older than 65 years and lenalidomide treatment will be long-lasting.

5.5 Prohibited Concomitant Therapy

Concomitant use of other lymphoma therapy or experimental therapies while the subject is on study drug is prohibited.

6 Efficacy and safety variables

6.1 Efficacy measures

6.1.1 Assessment of the disease status

Response to treatment is defined on the basis of International Workshop Response Criteria for non-Hodgkin's Lymphoma (Appendix E).

6.1.2 Survival status

Patient survival status will be determined every four weeks during the study treatment, every four months for three years after, every six months for the following two years and every year after there, until 10-year follow-up completion, progression or death.

In addition to reporting the serious adverse events, patient's deaths must be recorded continuously throughout the study.

Evaluation and documentation of the cause of death must be entered in the CRF.

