2.4 Secondary endpoints

- Overall survival (OS), response rate (RR), adverse events (AE) and serious adverse events (SAE) rate

3 Overall study design

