3.1 Type of study

This is an open label, single-arm, multicentre phase II trial evaluating the maintenance treatment of oral lenalidomide monotherapy given to patients with relapsed DLBCL who presented at least a PR to a second- or third-line therapy.

A total number of 47 eligible patients will be enrolled in the protocol and receive Lenalidomide 25 mg for 21 days every 28 days, until clinical appropriate. These subjects will be continuously monitored for safety, disease status and survival.

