8.2 Efficacy endpoints

8.2.1 Overall survival

It is defined as the time from enrolment to death for any cause. Patients alive at last follow-up will be censored.

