8.4 Efficacy analysis

Efficacy analyses will be performed on the intention-to-treat population that includes all subjects enrolled. Response rate during and after lenalidomide treatment will be provided. Analyses will be performed to characterize PFS, TTP and OS. The Kaplan-Meier procedure will be used to characterize the time-to-event curves in the analyses where there is censoring. Otherwise, summary statistics (mean, standard deviation, median, minimum and maximum) will be provided. Parameters known to be potentially predictive of disease aggressiveness and

OSPEDALE SAN RAFFAELE
ISTITUTO DI RICOVERO E CURA A CARATTERE SCIENTIFICO

likelihood of response to lenalidomide in relapsed or refractory DLBCLs (tumour burden, LDH levels, time from last rituximab, etc) as well as prognostic subtypes (namely “germinal-center B cell type” – GBC - and “activated B-cell type” – ABC) or specific gene expression patterns/genetic signatures amenable to DLBCL subtypes - where available - will be taken into consideration in post-hoc multivariate efficacy analysis.

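### Scheduled survival follow-up stops at progression (6.1.2) and participation ends at lymphoma failure (4.3.1), yet overall survival is time to death from any cause in all enrolled patients

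*Combined protocol and SAP*

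**What the plan says.** OS is among the secondary endpoints in section 2.4: "Overall survival (OS), response rate (RR), adverse events (AE) and serious adverse events (SAE) rate". Section 8.2.1 defines it: "It is defined as the time from enrolment to death for any cause. Patients alive at last follow-up will be censored". Section 8.4 sets the population and the method: "Efficacy analyses will be performed on the intention-to-treat population that includes all subjects enrolled", and "The Kaplan-Meier procedure will be used to characterize the time-to-event curves in the analyses where there is censoring".

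Two passages end data collection earlier than that definition needs:

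- Section 6.1.2 sets survival checks four-weekly on treatment, then four-monthly for three years, six-monthly for two, and then "every year after there, until 10-year follow-up completion, progression or death".
- Section 4.3.1 item 1 regularly terminates participation "In case of death or in case of lymphoma failure". Item 2 does the same when study drug is stopped for toxicity or an adverse event.

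Other passages point the other way:

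- Section 3.1: "These subjects will be continuously monitored for safety, disease status and survival".
- Section 6.1.2 itself adds, separately from SAE reporting, that "deaths must be recorded continuously throughout the study".
- Sections 6.5.4 and 6.5.5 list visits up to one year after lenalidomide is discontinued and then for years, without naming progression as a stop. They list examinations and disease status, but not survival status.

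**The concern.** A patient who has progressed is at higher risk of death than one who has not. If last follow-up falls at or near progression, Kaplan-Meier treats that patient as if the later risk of death were the same as for patients still in remission. The censoring is informative and the curve is too high.

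In a single-arm trial no control group shares the bias, so the OS curve would be read at face value. The synopsis also has a secondary objective on whether genetic alterations add prognostic information on survival, and that uses the same deaths. Centres can each follow a different passage in good faith, so the curve could mix follow-up rules. Deaths not sought after progression may not be recoverable at analysis.

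**Working it through.** **Text check.** The question is whether any passage sets a survival contact after progression.

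| Section | Stops at progression? | Sets a survival contact after it? |
|---|---|---|
| 6.1.2, schedule | Yes | No |
| 4.3.1 item 1 | Yes (lymphoma failure) | No |
| 6.1.2, recording of deaths | Not stated | No contact or procedure |
| 3.1 | Not stated | No contact or procedure |
| 6.5.4 and 6.5.5 | Not stated | Visits continue, but survival status is not listed |

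No passage says which governs.

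**Inputs for size.** The plan gives no OS figure to reproduce. From 8.1 come N = 47 and one-year PFS S = 0.30 (null) or 0.50 (alternative), taken here as alive and progression-free. Assumed, because the documents do not give them: share d of first failures that are deaths; median survival m (months) after progression; constant hazards.

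**Patients losing scheduled contact in year one** = 47 × (1 − S) × (1 − d), for d from 0.05 to 0.20:

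- S = 0.30: 47 × 0.70 × 0.95 = 31.3; 47 × 0.70 × 0.80 = 26.3.
- S = 0.50: 47 × 0.50 × 0.95 = 22.3; 47 × 0.50 × 0.80 = 18.8.

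So about 19–31 of 47.

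**One-year OS.** Per year, let h = −ln S, a = (1 − d)h and λ = 12 ln 2 / m.

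- True OS = S + a(e^−λ − e^−h)/(h − λ). When h = λ it is S + a·e^−h.
- Kaplan-Meier limit if everyone is censored at progression = e^(−dh) = S^d.

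Example, S = 0.30, d = 0.05, m = 6: h = 1.204, a = 1.144, λ = 1.386. True OS = 0.30 + 1.144 × (0.25 − 0.30)/(1.204 − 1.386) = 0.614. Kaplan-Meier limit = 0.30^0.05 = 0.942. Gap 0.328.

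| S | d | m | True OS | Censored at progression | Gap |
|---|---|---|---|---|---|
| 0.30 | 0.05 | 6 | 0.614 | 0.942 | 0.328 |
| 0.30 | 0.05 | 12 | 0.748 | 0.942 | 0.194 |
| 0.30 | 0.10 | 6 | 0.597 | 0.887 | 0.289 |
| 0.30 | 0.10 | 12 | 0.724 | 0.887 | 0.162 |
| 0.50 | 0.05 | 6 | 0.738 | 0.966 | 0.228 |
| 0.50 | 0.05 | 12 | 0.829 | 0.966 | 0.137 |
| 0.50 | 0.10 | 6 | 0.725 | 0.933 | 0.208 |
| 0.50 | 0.10 | 12 | 0.812 | 0.933 | 0.121 |

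The range is about 12–33 points, and it is an upper bound because it supposes that no death after progression is captured. Wider inputs (d 0.05–0.20, m 4–24) give 3–41 points. If the 30% and 50% count progression only, as 8.2.2 is worded, the total hazard becomes h/(1 − d). The gap is then about 13–34 points with the first inputs, and the patient count, 47 × (1 − d) × (1 − e^(−h/(1 − d))) for d 0.05–0.20, is about 22–32.

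**If 6.5.4 and then 6.5.5 are followed**, visits do not stop at progression, so there is no bias from this source at one or two years.

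**The case against.** The best defence is that the plan does mean to capture deaths after progression. Section 3.1 promises continuous monitoring of survival, the death-recording duty in 6.1.2 stands apart from SAE reporting, and 6.5.4 and 6.5.5 name no stop at progression. One can also parse 6.1.2 so that the closing clause limits only the yearly phase, leaving the earlier contacts intact. This has weight: it makes the text a conflict rather than a settled rule. It does not remove the conflict. None of these passages provides a survival contact after progression, none overrides 4.3.1 item 1, and the narrow parse of 6.1.2 still leaves participation ending at lymphoma failure.

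A reader might also infer more than the documents support:

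- *That OS is overstated whichever passage is followed.* It is not. Under 6.5.4 and 6.5.5 the bias is zero.
- *That deaths are captured only to 30 days after the last dose.* The 30-day limit in 6.2.1.2 concerns SAE reports, and that section also covers SAEs during the study and related ones at any time. The duty in 6.1.2 to record deaths is separate.
- *That 4.3.1 item 2 endangers the primary endpoint.* Sections 6.5.4 and 6.5.5 already provide disease evaluation after discontinuation, past the one-year landmark for anyone who stops in year one. What remains is the wording of item 2, which can be read as ending that follow-up.

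**Conclusion.** The concern holds as an internal conflict: the schedule in 6.1.2 and the termination rule in 4.3.1 item 1 do not deliver the data that the OS definition and analysis need. The effect on OS is upward or none, depending on which passage a centre follows. The text finding is firm. The size is only illustrative: at most about 12–33 points at one year if no death after progression is captured, and 19–31 of 47 patients without scheduled survival contact in year one. Both rest on assumed inputs and constant hazards.

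A reader might take this as a threat to the trial's conclusion. The documents do not support that. OS is secondary and descriptive, and the two-stage rule in 8.1 uses only one-year progression-free status. The point should be fixed, but it does not call the design into question.

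**What to change.** - **6.1.2:** delete progression as an end of survival-status follow-up, so that status is collected to death or 10 years.
- **4.3.1:** separate end of study treatment from end of study follow-up. State that neither lymphoma failure nor a toxicity stop ends survival follow-up, and that a toxicity stop does not end the disease evaluation already planned in 6.5.4 and 6.5.5.

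The sample size, the decision rule and treatment do not change. The cost is a wording amendment and a few more survival contacts per progressed patient. At the four-monthly interval already in 6.1.2, the expected number is 1/(e^(4 ln 2/m) − 1): 1.7 at m = 6 and 3.8 at m = 12, so about 2–4. Over m = 4–24 it is about 1–8. The median m is assumed.

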6.1.3 Central pathology review and cell of origin (COO) characterization

All the registered cases will undergo central pathology review.

OSPEDALE SAN RAFFAELE
ISTITUTO DI RICOVERO E CURA A CARATTERE SCIENTIFICO

Efficacy of the experimental therapy will be analysed stratifying registered patients according to their COO, namely “germinal-centre B cell type” and “activated B-cell type” subgroups. COO will be defined according immunohistochemical results of antibodies raised against CD20, CD3, CD10, bcl-6, MUM-1/IRF4, and bcl-2 molecules, using the Hans algorithm. This is a surrogate practical tool in confirming data generated by gene-expression profiling and could be applied also to tissue microarrays obtained by formalin-fixed, paraffin-embedded (FFPE) clinical cases of DLBCL. The limits in detecting the precise COO by means of immunohistochemistry will be overcome by using a validated gene-expression-profiling-based assay performed on NanoString’s nCounter® Analysis System, now available on FFPE pathological material. The correlation between COO in DLBCL subtypes and clinical efficacy will be studied in order to identify genetic predictors of successful response to therapy with lenalidomide.

In order to identify cases of “double expressor lymphomas” and “double hit lymphomas”, MYC will be added to the previously mentioned bcl-6 and bcl-2 markers on FFPE samples by immunohistochemistry; these data will enable to select a subgroup of cases suitable for the assessment of MYC and BCL2 genetic abnormalities through FISH technique.

Cereblon (CRBN), a substrate receptor of the E3 ubiquitin ligase complex CRL4CRBN, is the target of lenalidomide. Expression of cereblon will be evaluated in diagnostic tissue samples by immunohistochemistry, through the use of a Celgene anti-CRBN rabbit monoclonal antibody CRBN65. The prognostic value of the expression of CRBN will be assessed on the clinical data from registered patients.

In order to fulfil these aims, diagnostic tissue blocks (tissue block from biopsy performed at relapse is also requested if available) and all the diagnostic, already stained specimens per case should be referred to: [name], Pathology Unit, IRCCS San Raffaele Scientific Institute, [name] ([contact] – e-mail: [contact]). In the case the blocks will not be available, all stained specimens plus 30 unstained slides, prepared as to undergo antigen retrieval, will be referred for analyses; in the case stained slides and blocks will not be available, one Haematoxylin and eosin plus 40 unstained slides, prepared as to undergo antigen retrieval, will be referred.

6.2 Safety measures

6.2.1 Adverse events

6.2.1.1 Adverse Event Definitions and Classifications

Timely, accurate, and complete reporting and analysis of safety information from clinical studies are crucial for the protection of subjects and investigators and are mandated by Regulatory Agencies worldwide.

- *Adverse Event*

An adverse event (AE) is any untoward medical occurrence in a clinical investigation subject administered a pharmaceutical product. An adverse event does not necessarily have a causal relationship with the treatment. An adverse event can therefore be any unfavorable and unintended sign (including an abnormal laboratory finding), symptom, or disease temporally associated with the use of an investigational medicinal product, whether or not considered related to the investigational medicinal product (Definition per International Conference on Harmonization [ICH]).

This includes any occurrence that is new in onset or aggravated in severity or frequency from the baseline condition, or abnormal results of diagnostic procedures, including laboratory test abnormalities.

Note: The Investigator collect adverse events starting from the time of signing the informed consent through the end of the designated follow-up period.

Abnormal laboratory values defined as adverse events

An abnormal laboratory value is considered to be an AE if the laboratory abnormality is characterized by any of the following:

- results in discontinuation from the study
- requires treatment, modification/interruption of study drug dose, or any other therapeutic intervention
- is judged by the Investigator to be significant clinical importance

If a laboratory abnormality is one component of a diagnosis or syndrome, then only the diagnosis or syndrome should be recorded on the AE page of the CRF. If the abnormality was not part of a diagnosis or syndrome, then the laboratory abnormality should be recorded as the AE.

- *Serious Adverse Event*

A serious adverse event (SAE) as defined by ICH is any untoward medical occurrence that at any dose:

- results in death
- is life-threatening (the subject was at risk of death at the time of the event. It does not refer to an event that hypothetically might have caused death if it were more severe).
- results in persistent or significant disability/ incapacity, or
- is a congenital anomaly/birth defect

OSPEDALE SAN RAFFAELE
ISTITUTO DI RICOVERO E CURA A CARATTERE SCIENTIFICO

Note: Medical and scientific judgment should be exercised in deciding whether expedited reporting is also appropriate in situations other than those listed above. For example, important medical events may not be immediately life-threatening or result in death or hospitalization, but may jeopardize the subject or may require intervention to prevent one of the outcomes listed in the definition above. Any adverse event is considered a serious adverse event if it is associated with clinical signs or symptoms judged by the investigator to have a significant clinical impact. Events not considered to be SAEs are hospitalizations which: were planned before entry into the clinical study; are for elective treatment of a condition unrelated to the studied indication or its treatment; occur on an emergency outpatient basis and do not result in admission (unless fulfilling other criteria above); are part of the normal treatment or monitoring of the studied indication and are not associated with any deterioration in condition.

If an AE is considered serious, both the AE pages of the CRF and the SAE Report form must be completed.

For each SAE, the investigator will provide information on severity, start and stop dates, relationship to (investigational product) study drug, action taken regarding (investigational product) study drug and outcome.

- *Classification of severity*

For both AEs and SAEs, the investigator(s) must assess the severity of the event. The severity of adverse events (AEs) will be graded on a scale of 1 to 5 according to the National Cancer Institute (NCI) Common Terminology Criteria for Adverse Events Version 3.0 (NCI CTCAE). The NCI CTCAE V3.0 can be viewed on-line at the following NCI web site: <http://ctep.cancer.gov/reporting/ctc.html>. If a specific event is not included in the NCI CTCAE toxicity scale, the following scale should be used to grade the event

Grade Definition:

- 1 **Mild** Awareness of sign, symptom, or event, usually transient, requiring no special treatment and generally not interfering with usual daily activities
- 2 **Moderate** Discomfort that causes interference with usual activities; usually ameliorated by basic therapeutic manoeuvres
- 3 **Severe** Incapacitating with inability to do usual activities or significantly affects clinical status and warrants intervention. Hospitalization may or may not be required
- 4 **Life-threatening** Immediate risk of death; requires hospitalization and clinical intervention.
- 5 **Death**

- *UnexpectedAdverse Event*

An adverse event, the nature or severity of which is not consistent with the applicable product information (for an investigational medicinal product, the Investigator's Brochure). *Associated With the Use of the Investigational medicinal product*

An adverse event is considered associated with the use of the investigational product if the attribution is possible, probable, or very likely by the definitions listed in Section 10.1.2.

Attribution Definitions

- Not related.

An adverse event that is not related to the use of the investigational product.

- Doubtful.

An AE for which an alternative explanation is more likely, e.g., concomitant drug(s), concomitant disease(s), or the relationship in time suggests that a causal relationship is unlikely.

- Possible.

An AE that might be due to the use of the investigational product. An alternative explanation, e.g., concomitant drug(s), concomitant disease(s), is inconclusive. The relationship in time is reasonable; therefore, the causal relationship cannot be excluded.

- Probable.

An AE that might be due to the use of the investigational product. The relationship in time is suggestive (e.g., confirmed by dechallenge). An alternative explanation is less likely, e.g., concomitant drug(s), concomitant disease(s).

- Very likely.

An AE that is listed as a possible adverse event reaction, and cannot be reasonably explained by an alternative explanation, e.g., concomitant investigational drug(s), concomitant disease(s). The relationship in time is very suggestive (e.g., it is confirmed by dechallenge and rechallenge).

Classification of Relationship/Causality of adverse events (SAE/AE) to study drug

The Investigator(s) must determine the relationship between the administration of study drug and the occurrence of an AE/SAE as Not Suspected or Suspected as defined below:

Not suspected:

The temporal relationship of the adverse event to study drug administration makes a causal relationship unlikely or remote, or other medications, therapeutic interventions, or underlying conditions provide a sufficient explanation for the observed event

Suspected:

The temporal relationship of the adverse event to study drug administration makes a causal relationship possible, and other medications, therapeutic interventions, or

underlying conditions do not provide a sufficient explanation for the observed event.

Treatment-related mortality

If an adverse event considered associated with the study medication results in a patient's death, then the event will be listed as a "treatment-related mortality".

Procedures

All Adverse Events

All AEs, with the exception of progression of systemic AL-amyloidosis, that occur between the first study-related procedures and for 30 days following the last dose of investigational product will be reported. Resolution information after 30 days should also be provided for grade 3 to 4 drug related events. This subset should be followed up until resolution to a grade 1 or better.

Adverse events occurring after 30 days should also be reported if considered related to investigational product.

Clinically relevant changes in laboratory values must be recorded in the adverse event section of the CRF.

All AEs, regardless of seriousness, severity, or presumed relationship to study therapy, must be recorded in the source document and the CRF. Investigators must record in the CRF their opinion concerning the relationship of the adverse event to the study therapy. All measures required for adverse event management must be recorded in the source document.

The Principal Investigator assumes responsibility for appropriate reporting of adverse events to the regulatory authorities. The Principal Investigator must report these events to the appropriate Institutional Review Board (IRB) that approved the protocol unless otherwise required and documented by the IRB.

Serious Adverse Event (SAE) Reporting Report of Adverse Events to Regulatory Authorities and the Ethics Committee

The sponsor will inform relevant Regulatory Authorities and the Ethics Committee:

- of all relevant information about serious unexpected adverse events suspected to be related to the study medication that are fatal or life threatening as soon as possible, and in any case no later than seven days after knowledge of such a case. Relevant follow-up information for these cases will subsequently be submitted within an additional eight days.
- of all other serious unexpected events suspected to be related to the study medication as soon as possible, but within a maximum of fifteen days of first knowledge by the investigator.

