8.3 Safety endpoints

8.3.1 Grade 3-4 NCI-CTC AEs

All NCI-CTCAE grade 3-4 will be recorded.

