8.5 Safety analysis

All subjects who receive at least one week of study drug medication will be included in safety analysis. AEs, vital signs measurements, clinical laboratory information and concomitant medications will be tabulated and summarized. Subject incidence rates of all AEs and events requiring the discontinuation of study drug will be tabulated by system class, preferred term, and severity using MedDRA terms and NCI-CTCAE Version 3.0 severity grades. Time to first dose reduction will be summarized for each regimen. Death and clinically important AEs (including tumour lysis and thrombosis) will also be summarized.

All other measurements will be summarized using means, standard deviations, medians, minimum and maximum. Graphical display will be provided where useful in the interpretation of results.

9 Data handling and record keeping

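### The laboratory-AE rule has no grade threshold and conflicts with the commitment to record all grade 3-4 events, so grade 3-4 cytopenias may be under-counted

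*Combined protocol and SAP*

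**What the plan says.** Section 6.2.1.1 has a paragraph on when a laboratory value counts as an adverse event: "An abnormal laboratory value is considered to be an AE if the laboratory abnormality is characterized by any of the following". Three alternatives follow:

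- The first is that the patient comes off study because of the value.
- The second is that the value "requires treatment, modification/interruption of study drug dose, or any other therapeutic intervention".
- The third rests on opinion, namely that the value "is judged by the Investigator to be significant clinical importance".

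The reporting procedures later in that section use a similar test: "Clinically relevant changes in laboratory values must be recorded in the adverse event section of the CRF". Clinical relevance is not defined.

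Other text is wider. The general AE definition in 6.2.1.1 covers anything new or worse than baseline, "or abnormal results of diagnostic procedures, including laboratory test abnormalities". Section 5.3 has AEs evaluated at every visit under CTCAE version 3.0 and gives numeric grade limits for platelets, haemoglobin and neutrophils. Section 8.3.1, which is headed as an endpoint of grade 3-4 AEs, says "All NCI-CTCAE grade 3-4 will be recorded".

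On analysis, section 8.5 tabulates AE incidence by MedDRA term and CTCAE severity. It also commits to tabulating laboratory information, without giving a format. For the rest it says "All other measurements will be summarized using means, standard deviations, medians, minimum and maximum". Blood counts and biochemistry are scheduled weekly for eight weeks and fortnightly after that (6.5.3).

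**The concern.** Two rules govern the same event. One admits a laboratory value through action or judgement; the other takes in every grade 3-4 event. A grade 3 neutropenia that appears on a scheduled count and recovers without intervention can fail the first and still fall under the second. Because severity grade is tabulated for AEs only, no planned table is certain to count it.

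Safety is the first-listed secondary objective (2.2), and cytopenias are prominent among the grade 3-4 toxicities that the protocol cites for this drug (1.2, 1.3). The trial is multicentre (3.1), so centres could follow different parts of the text and all be compliant. The reported cytopenia rate would then depend partly on local recording practice.

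**Working it through.** The plan gives no figure to reproduce here. The check is a side-by-side reading, followed by a scale illustration.

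**1. The rules applied to one case.** Take a grade 3-4 count on a scheduled visit, with no action taken and not judged important.

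| Text | Is it recorded as an AE? |
|---|---|
| 6.2.1.1, general AE definition | Yes, if new or worse than baseline |
| 6.2.1.1, laboratory-value criteria | Meets none of the three |
| 6.2.1.1, reporting procedures | Only if considered clinically relevant |
| 5.3, evaluation at each visit | Supplies a grade; does not say that a graded value is automatically an AE |
| 8.3.1 | Yes |

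The entry limits sharpen the conflict. Section 4.2 excludes neutrophils below 1000/μL, platelets below 75,000/mm³ and haemoglobin below 9 g/dL. Grade 3 in section 5.3 starts below 1000 for neutrophils (taken per μL), below 50 × 10^9/L for platelets and below 8 g/dL for haemoglobin. Relative to the entry limits, any on-study grade 3-4 value is therefore new or worse. The general definition would take in all of them; the three criteria would not.

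**2. A second route out of the table.** Section 6.2.1.1 also says that an abnormality forming part of a diagnosis or syndrome is entered only under that diagnosis. A cytopenia that was acted on can then disappear as a graded laboratory term.

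**3. Available data.** If the 6.5.3 schedule runs for all 24 four-week cycles, treatment lasts 24 × 4 = 96 weeks. Counts per patient are 8 + (96 − 8)/2 = 52, or 47 × 52 = 2,444 for 47 full-course patients. Means, medians and a cohort minimum of these values do not give the number of patients who reached grade 3-4.

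**4. Scale, for illustration.** Let p be the true patient-level rate and e the share of affected patients who escape the AE filter. Then reported rate = p × (1 − e), and patients missed = 47 × p × e. The value of e is an assumption; the documents do not give it. For p, I use two rates that the protocol cites: grade 3 neutropenia of 14% in the earlier lymphoma study (1.3; 47 × 0.14 = 6.6 patients) and grade 3-4 neutropenia of 53.4% in the MDS study (1.2; 47 × 0.534 = 25.1 patients).

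| e | p = 14%: reported (missed) | p = 53.4%: reported (missed) |
|---|---|---|
| 0 | 14% (0) | 53.4% (0) |
| 0.10 | 12.6% (0.7) | 48.1% (2.5) |
| 0.25 | 10.5% (1.6) | 40.1% (6.3) |
| 0.50 | 7% (3.3) | 26.7% (12.5) |

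The filter can only remove cases, so the reported rate cannot exceed the true one through this route.

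**5. Units.** Section 5.3 labels neutrophils as ANC per μL but attaches × 10^9/L to each limit. Since 1 × 10^9/L equals 1000/μL, the two readings differ by a factor of 1,000. A grading program needs one of them settled.

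**The case against.** The strongest reply is that this is a conflict of wording with no demonstrated loss of data. The laboratory rule is phrased with a plain conditional, not as an exclusive condition. The general definition, section 5.3 and section 8.3.1 all point towards capture, and a centre that follows them would record these cytopenias. That stands. It rules out the stronger reading, which a reader might infer, that a laboratory value becomes an AE only through the three criteria and that the endpoint therefore does miss measured cytopenias. It does not remove the conflict: if every abnormality already counted, the three criteria would have no function.

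Other parts of the reply also stand:

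- Cytopenias that lead to treatment, interruption or a dose change are AEs under the second criterion. If Appendix I ties grade 3-4 counts to such action, little or nothing is lost, so zero belongs in the range.
- Section 8.3.1 is not the only safety endpoint; section 2.4 also lists AE and SAE rates.
- Section 8.5 does tabulate laboratory information. What it lacks is a grade-based format.
- The cited neutropenia rates are described as events or adverse events, and the documents do not say how they were ascertained. They serve as illustrations of scale, not as laboratory-derived truth.
- Safety is descriptive here. No threshold or test uses the grade 3-4 rate, and the decision on one-year PFS is unaffected.

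On cost, section 9.3 describes handwritten CRFs kept at the centres, so transcribing some 2,444 counts could be a burden. That objection is largely met by section 8.5, which already commits the trial to tabulating laboratory data.

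**Conclusion.** The point holds as an inconsistency with a possible downward error. The action-or-judgement rule in 6.2.1.1 does not agree with section 8.3.1 or with the wider definition in its own section, and section 8.5 specifies no grade table from laboratory values that would make the disagreement harmless. Measured grade 3-4 cytopenias that are neither acted on nor judged important may be left out of the incidence, and centres may differ.

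The size is unknown. Under the assumed range of 0% to 50% escaping, an illustrative 14% becomes 14% to 7%, which is 0 to 3.3 patients of 47. The supplied text gives no basis for a narrower range or for one that excludes zero. A reader might also infer that the trial's rates could not be compared with those cited in sections 1.2 and 1.3. The documents support only that comparability is not assured either way.

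**What to change.** 1. Reconcile section 5.3, the three statements in 6.2.1.1 (general definition, laboratory criteria, reporting procedures) and section 8.3.1, so that one rule says whether a grade 3-4 laboratory value is recorded as an AE.
2. Reconcile the neutrophil units in section 5.3 before any grading is programmed.
3. In sections 8.3.1 and 8.5, add a table of worst CTCAE version 3.0 grade per patient and per cycle, with shift from baseline, derived from the recorded blood count and biochemistry values whether or not an AE was entered. Report it beside the AE-based incidence, so that both counts are visible and neither replaces the other.

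The cost is one derived table from tests already scheduled and values already due to be tabulated, with no new visits or tests. The reported toxicity rates may become less favourable.
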